**ABBREVIATIONS**

AE	adverse event
ANCOVA	analysis of covariance
CI	confidence interval
CRF	case report form
CSR	Clinical Study Report
DBL	database lock
DC	Discontinuation
ECG	Electrocardiogram
eCRF	electronic case report form
eC-SSRS	Electronic Columbia-Suicide Severity Rating Scale
FDA	Food and Drug Administration
IGA	Investigator's Global Assessment
IgG1 $\lambda$	immunoglobulin G1 lambda
IWRS	interactive web response system
mAb	monoclonal antibody
MedDRA	Medical Dictionary for Regulatory Activities
NABs	neutralizing antibodies
PASI	Psoriasis Area and Severity Index
PD	Pharmacodynamic
PK	pharmacokinetic(s)
PQCs	product quality complaints
SAE	serious adverse event
SAP	Statistical Analysis Plan
SD	standard deviation
SIAQ	Self-Injection Assessment Questionnaire

## 1. INTRODUCTION

This statistical analysis plan (SAP) contains definitions of analysis sets, derived variables, and statistical methods for the analyses of efficacy, safety and pharmacokinetics for the guselkumab (CNTO 1959) clinical study CNTO1959PSO3006. Guselkumab is a fully human immunoglobulin G1 lambda (IgG1 $\lambda$ ) monoclonal antibody (mAb) that inhibits the biological activity of IL-23 and therefore has the potential for the treatment of psoriasis.

### 1.1. Trial Objectives

#### Primary Objectives

The primary objectives are:

- To evaluate the efficacy of guselkumab delivered using the SelfDose device for the treatment of subjects with moderate to severe plaque-type psoriasis.
- To assess the safety and tolerability of guselkumab delivered using the SelfDose device in subjects with moderate to severe plaque-type psoriasis.

#### Secondary Objectives

The secondary objectives are:

- To assess the PK and immunogenicity of guselkumab following SC administration using the SelfDose device in subjects with moderate to severe plaque-type psoriasis.
- To assess usability and acceptability of the SelfDose device.

### 1.2. Trial Design

This is a Phase 3, randomized, double-blind, multicenter, placebo-controlled study evaluating the efficacy, safety, PK, immunogenicity, usability, and acceptability of guselkumab delivered using the SelfDose device in subjects with moderate to severe plaque-type psoriasis. The target population is adult men or women, with a diagnosis of plaque-type psoriasis (with or without PsA) for at least 6 months before the first administration of study drug. Subjects must have moderate to severe plaque-type psoriasis defined by PASI  $\geq 12$ , IGA  $\geq 3$ , and involved body surface area (BSA)  $\geq 10\%$ . Subjects must be candidates for either systemic therapy or phototherapy for psoriasis, and may have previously received some systemic therapies (Protocol Inclusion Criteria, Exclusion Criteria) or phototherapy for psoriasis. Subjects with nonplaque forms of psoriasis (eg, erythrodermic, guttate, or pustular) or with drug-induced psoriasis (eg, a new onset of psoriasis or an exacerbation of psoriasis from beta blockers, calcium channel blockers, or lithium) are excluded. Subjects who have ever received guselkumab are also excluded.

Approximately 75 subjects who satisfy all inclusion and exclusion criteria will be randomized in a 4:1 ratio to 1 of 2 arms:

[figure not shown]
- **Group I** (n=60): guselkumab 100 mg at Weeks 0, 4, 12, 20, and 28; placebo at Week 16 to maintain the study blind.
- **Group II** (n=15): placebo at Weeks 0, 4, and 12; cross over to guselkumab 100 mg at Weeks 16, 20, and 28.

Week 28 is the last dosing visit; subjects will be followed for an additional 12 weeks and have a final safety visit at Week 40. The end of the study is defined as the time when last subject completes the Week 40 visit.

There are 2 database locks (DBLs) in this study, 1 at Week 20, and 1 at Week 40.

A diagram of the study design is provided below.

**Schematic Overview of the Guselkumab SelfDose Device Study**

**1.3. Statistical Hypotheses for Trial Objectives**

Primary Hypotheses:

The primary hypotheses are that guselkumab treatment delivered using the SelfDose device is superior to placebo as demonstrated by 1) the proportion of subjects achieving an IGA score of cleared (0) or minimal (1) at Week 16; and 2) the proportion of subjects achieving a PASI 90 response at Week 16.

Major secondary hypotheses:

- Guselkumab treatment delivered using the SelfDose is superior to placebo as assessed by the proportion of subjects achieving an IGA score of cleared (0) at Week 16.
- Guselkumab treatment delivered using the SelfDose is superior to placebo as assessed by the proportion of subjects achieving a PASI 100 response at Week 16.

#### 1.4. Sample Size Justification

This study is designed to evaluate the efficacy of guselkumab vs placebo using the SelfDose device.

The assumptions for the sample size and power calculations are based on the data from the guselkumab CNTO1959PSO2001 study:

- The proportion of placebo subjects who achieved a PGA score of cleared (0) or minimal (1) and a PASI 90 response was 10% and 5%, respectively. Note PGA was used in CNTO1959PSO2001. PGA is a similar measure to IGA which will be used in this study.
- The proportion of subjects who achieved a PGA score of cleared (0) or minimal (1) response at Week 16 was 86% in the guselkumab 100 mg group.
- The proportion of subjects who achieved a PASI 90 response at Week 16 was 62% in the guselkumab 100 mg group.

As shown in the table below, based on the above assumptions, with a total of approximately 75 subjects randomized in a 4:1 ratio to guselkumab 100 mg (n=60) and placebo (n=15), there will be at least 99% power to detect differences for both co-primary endpoints in the proportion of subjects achieving an IGA score of cleared (0) or minimal (1) and the proportion of subjects who achieve a PASI 90 response between the placebo and guselkumab groups at Week 16, at a significance level of 0.05. This sample size was also chosen to provide adequate power for major secondary endpoints.

**Table 1: Power to Detect a Treatment Effect Based on Different Proportions of Subjects Achieving the Co-primary Endpoints**

Co-primary Endpoints		Power
IGA cleared (0) or minimal (1) response at Week 16		
Placebo (n=15) 10%	Guselkumab 100 mg q8w (n=60) 70%	>99%
	75%	>99%
	80%	>99%
PASI 90 response at Week 16		
Placebo (n=15) 5%	Guselkumab 100 mg q8w (n=60) 55%	99%
	60%	>99%
	65%	>99%

IGA=Investigator's Global Assessment; PASI=Psoriasis Area and Severity Index; q8w=every 8 weeks.

## **1.5. Randomization and Blinding**

### **1.5.1. Procedures for Randomization and Stratification**

Central randomization will be implemented in this study. At Week 0, subjects will be randomly assigned to 1 of 2 treatment groups based on a computer-generated randomization schedule prepared under the supervision of the sponsor. Permuted block randomization with stratification by country will be used. The interactive web response system (IWRS) will assign a unique treatment code, which will dictate the treatment assignment and matching study drug kit for the subject. The requestor must use his or her own user identification and personal identification number when contacting the IWRS, and will then give the relevant subject details to uniquely identify the subject.

### **1.5.2. Blinding**

The investigator will not be provided with randomization codes. The codes will be maintained within the IWRS, which has the functionality to allow the investigator to break the blind for an individual subject.

Data that may potentially unblind the treatment assignment (eg, study drug serum concentrations, antibodies to study drug, treatment allocation) will be handled with special care to ensure that the integrity of the blind is maintained and the potential for bias is minimized. This can include making special provisions, such as segregating the data in question from view by the investigators, clinical team, or others as appropriate until the time of DBL and unblinding.

Under normal circumstances, the blind should not be broken to subjects, investigators, or site monitors until the Week 40 database is locked and finalized. Otherwise, the blind should be broken only if specific emergency treatment/course of action would be dictated by knowing the treatment status of the subject. In such cases, the investigator may in an emergency determine the identity of the treatment by contacting the IWRS. It is recommended that the investigator contact the sponsor or its designee if possible to discuss the particular situation, before breaking the blind. Telephone contact with the sponsor or its designee will be available 24 hours per day, 7 days per week. In the event the blind is broken, the sponsor must be informed as soon as possible. The date of unblinding must be documented by the IWRS, in the appropriate section of the electronic case report form (eCRF), and in the source document; the reason for unblinding must be documented in the appropriate section of the eCRF and in the source document. The documentation received from the IWRS indicating the code break must be retained with the subject's source documents in a secure manner.

Subjects who have had their treatment assignment unblinded should continue to return for scheduled evaluations. The decision to continue or discontinue study treatment for these subjects will be based upon consultation of the investigator with the medical monitor.

There are 2 DBLs in this study, 1 at Week 20, and 1 at Week 40. The sponsor, with exception of sponsor site monitors noted below, will be unblinded after the last subject has completed the Week 20 visit and the Week 20 DBL has occurred. The investigators, subjects, and sponsor site monitors will be unblinded after the last subject has completed the Week 40 visit, and the Week 40 DBL has occurred.

## 2. GENERAL ANALYSIS DEFINITIONS

This analysis plan provides the general analysis definitions and describes the planned subject information, efficacy, safety, pharmacokinetics, and antibody analyses for the two planned DBLs.

### 2.1. Imputation Rules for Partial or Missing AE Dates

Partial AE onset dates will be imputed as follows:

- If the onset date of an adverse event is missing day only, it will be set to:
  - First day of the month that the AE occurred, if month/year of the onset of AE is different than the month/year of the study agent start
  - The day of study agent start, if the month/year of the onset of AE is the same as month/year of the study agent start date and month/year of the AE resolution date is different
  - The day of study agent start or day of AE resolution date, whichever is the earliest, if month/year of the onset of AE and month/year of the study agent start date and month/year of the AE resolution date are same
- If the onset date of an adverse event is missing both day and month, it will be set to the earliest of:
  - January 1 of the year of onset, as long as this date is on or after the study agent start date
  - Month and day of the study agent start date, if this date is in the same year that the AE occurred
  - Last day of the year if the year of the AE onset is prior to the year of the study agent start date,
  - The AE resolution date.

Completely missing onset dates will not be imputed.

Partial AE resolution dates not marked as ongoing will be imputed as follows:

- If the resolution date of an adverse event is missing day only, it will be set to the earliest of the last day of the month of occurrence of resolution or the day of the date of death, if the death occurred in that month.
- If the resolution date of an adverse event is missing both day and month, it will be set to the earliest of December 31 of the year or the day and month of the date of death, if the death occurred in that year.

Completely missing resolution dates will not be imputed.

### 2.2. Visit Windows

Nominal visits will be used for all by-visit analyses in the study unless otherwise specified, regardless of the scheduled visit window. The study visits scheduled should occur at the times delineated in the Time and Events Schedule of the protocol. All visits through Week 32 should occur within  $\pm 7$  days of the scheduled visit. If a study visit occurs outside this window, the

sponsor should be consulted about how the subject should resume his/her normal dosing schedule relative to the baseline visit (Week 0). The Week 40 study visit should occur within +14 days of the scheduled visit.

## **2.3. Analysis Sets**

### **2.3.1. Efficacy Analysis Set**

For the efficacy analyses in this study, the full analysis set (FAS) will be used according to subjects' assigned treatment to which they were randomized, regardless of the treatment they actually received. The FAS includes all randomized subjects who received at least 1 injection of study agent. The full analysis set will be used for all primary and secondary efficacy analyses.

For subjects randomized to placebo, only subjects who crossed over to receive guselkumab at Week 16 will be included in the efficacy summaries for the visits after Week 16.

### **2.3.2. Safety Analysis Set**

In contrast to the efficacy analysis set, safety analyses will be performed on the safety analysis set, which is defined as all randomized and treated subjects who received at least 1 injection of study agent (partial or complete) according to the actual treatment received during the study irrespective of the treatment assigned at randomization.

### **2.3.3. Pharmacokinetics Analysis Set**

The PK analysis set is defined as subjects who received at least one injection of guselkumab and have at least one valid blood sample drawn for PK analysis.

### **2.3.4. Immunogenicity Analysis Set**

The immunogenicity analysis set is defined as all subjects who received at least one injection of guselkumab and have appropriate samples for anti-guselkumab antibody detection.

In both PK and immunogenicity analyses, subjects will be analyzed according to the treatment they actually received, regardless of the treatments they are randomized to.

## **2.4. Definition of Subgroups**

To evaluate the consistency of efficacy based on demographic characteristics, baseline disease characteristics, and psoriasis medication history, subgroup analyses will be performed for the co-primary endpoints. The subgroups for subgroup analyses include the following:

### **Baseline demographics:**

- Sex (male, female)
- Race

- Baseline Age (<45 years, 45 to <65 years, ≥65 years)
- Baseline weight (≤90 kg, >90 kg)
- BMI (Normal [<25], Overweight [25 -<30], Obese [≥30])

**Baseline disease characteristics:**

- Age at diagnosis (years) (<25, ≥25)
- Psoriasis disease duration (years) (<15, ≥15)
- Baseline PASI (<20, ≥20)
- Baseline IGA (<4, =4)
- Baseline BSA (<20%, ≥20%)
- Psoriatic arthritis (Yes, No)

**Psoriasis medication history:**

- Phototherapy (ultraviolet B light [UVB] or psoralen and ultraviolet A light therapy [PUVA])
  - Never used
  - Ever used
- Non-biologic systemics (PUVA, MTX, cyclosporine, acitretin, apremilast, or tofacitinib)
  - Never used
  - Ever Used
- Biologics (etanercept, infliximab, alefecept, efalizumab, ustekinumab, briakinumab, secukinumab, ixekizumab, brodalumab, or adalimumab)
  - Never used
  - Ever Used
- Non-biologic systemics or biologics (as defined above)
  - Never used
  - Ever used

**2.5. Statistical Methods****2.5.1. Study Day**

Study Day 1 refers to the first study agent administration date. The study day for an event is defined as:

- Event date - (date of Study Day 1) +1, if event date is ≥ date of Day 1
- Event date - date of Day 1, if event date < date of Day 1

## 2.5.2. Baseline

In general, the baseline measurement is defined as the closest measurement taken prior to or at the time of the first study agent administration date unless otherwise specified.

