#### **4.4. Extent of Exposure**

The exposure data will be summarized through Week 20 and through Week 28. The number and percentage of subjects who receive study agent will be summarized by treatment group for the safety analysis set. Descriptive statistics will be presented for the following parameters:

- Number of injections
- Cumulative total dose

In addition, the study agent lots received by treatment, including matching placebo for active treatment will be summarized.

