#### **Summaries through Week 20 or through Week 40**

Safety data through Week 20 and through Week 40 will be summarized by treatment group defined as follows:

1. **Placebo → Guselkumab 100 mg:** all subjects who were randomized to placebo at Week 0, started treatment with placebo only, and later crossed over to receive treatment with guselkumab. Only the safety events/measurements from these subjects that occurred on or after their first administration of guselkumab 100 mg will be included in this group.
2. **Guselkumab 100 mg:** all subjects who were randomized to guselkumab 100 mg at Week 0 and received study agent with guselkumab 100 mg. All the safety events/measurements from these subjects that occurred beginning at Week 0 will be included in this group.

3. **Combined Guselkumab 100 mg:** all subjects as described above in the Placebo → Guselkumab 100 mg and the Guselkumab 100 mg groups.

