## 7.2. Clinical Laboratory Tests

All clinical laboratory reports will be displayed for the subjects included in the safety analysis set. The clinical laboratory parameters to be evaluated by the central laboratory include but are not limited to:

- **Hematology:** hemoglobin, hematocrit, lymphocytes, neutrophils, platelets, red blood cell (RBC) count and white blood cell (WBC) count.
- **Chemistry:** albumin, alkaline phosphatase, alanine aminotransferase, aspartate aminotransferase, total carbon dioxide (CO2), total bilirubin, blood urea nitrogen/urea, calcium, chloride, creatinine, glucose, potassium, total protein, sodium.

Box plots of laboratory measurements and change from baseline will be provided for selected laboratory analytes.

Applicable laboratory results will be graded according to National Cancer Institute's Common Terminology Criteria for Adverse Events (NCI-CTCAE version 4.03). The worst NCI-CTCAE will be summarized by treatment group.

For nonfasting glucose, the screening measurement will be used as the baseline measurement. A listing of subjects with 1 or more NCI-CTCAE toxicity grade  $\geq 2$  abnormalities in hematology and clinical chemistry laboratory measurements will be provided.

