## 7.3. Vital Signs

Vital signs variables including respiratory rate, blood pressure (systolic and diastolic) will be measured at visits as per the time and events schedule in the protocol. Descriptive statistics of the observed value and change from baseline of the vital signs will be summarized by treatment group.

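### Post-crossover laboratory and vital-sign change is measured from a pre-placebo baseline, so the guselkumab columns through Weeks 20 and 40 include change that arose on placebo

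*SAP*

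**What the plan says.** - **Baseline (SAP 2.5.2).** The rule opens "In general, the baseline measurement is defined as" and fixes the reference value as follows: "the baseline measurement is defined as the closest measurement taken prior to or at the time of the first study agent administration date". It yields wherever another section specifies something different.
- **Study agent covers placebo.** SAP 2.3.1 defines the efficacy set, which contains the placebo arm, by receipt of study agent: "The FAS includes all randomized subjects who received at least 1 injection of study agent". SAP 4.4 says that "the study agent lots received by treatment, including matching placebo for active treatment will be summarized".
- **Group II schedule (SAP 1.2).** "placebo at Weeks 0, 4, and 12; cross over to guselkumab 100 mg at Weeks 16, 20, and 28".
- **Columns through Week 20 and Week 40 (SAP 7).** For the Placebo → Guselkumab column: "Only the safety events/measurements from these subjects that occurred on or after their first administration of guselkumab 100 mg will be included in this group". The Combined Guselkumab column pools these subjects with those on guselkumab from Week 0.
- **Outputs that use change.** SAP 7.3: "Descriptive statistics of the observed value and change from baseline of the vital signs will be summarized by treatment group". SAP 7.2: "Box plots of laboratory measurements and change from baseline will be provided for selected laboratory analytes".
- **Special safety baselines.** Nonfasting glucose uses the screening value (SAP 7.2). The eC-SSRS uses the worse of screening and Week 0 (SAP 7.4.1). Both precede the first placebo injection.

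**The concern.** The Week 20 and Week 40 columns are built on exposure: a crossover subject contributes only from the first guselkumab injection. The reference value subtracted from those measurements was taken before the first placebo injection, 16 weeks earlier. The measurement is filtered by guselkumab exposure and the baseline is not.

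Anything that moved a laboratory value or vital sign during the placebo period therefore appears as change in a guselkumab column. A placebo-period movement in the opposite direction could equally offset a change that began after crossover. Safety is one of the two primary objectives, and with no formal safety comparison planned, readers depend on each descriptive column meaning what its heading suggests. The Placebo → Guselkumab heading at least shows the history. The Combined Guselkumab heading does not.

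**Working it through.** The SAP states no figure on this point, so there is none to reproduce. The check follows the baseline rule through to the outputs.

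**Inputs.** Planned allocation is 60 guselkumab and 15 placebo, 75 in all. First guselkumab in Group II is at Week 16 (both SAP 1.2). Baseline is at or before the first study agent injection (SAP 2.5.2).

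**Step 1: which baseline applies.** Study agent includes placebo (SAP 2.3.1 and 4.4), so for Group II the baseline is at or before Week 0. The two special safety baselines are also pre-placebo. No section sets a Week 16 baseline.

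**Step 2: what the reported change contains.** Write Y(t) for the value at week t, with Y(0) the baseline. For a crossover subject at a visit after Week 16:

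reported change = Y(t) − Y(0) = [Y(16) − Y(0)] + [Y(t) − Y(16)]

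The first bracket arose wholly on placebo. Only the second follows the start of guselkumab.

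**Step 3: effect on column means.** Let d be the mean of Y(16) − Y(0) among crossover subjects. The SAP gives no value for d.

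- Placebo → Guselkumab column: d enters the mean change in full.
- Combined column, with k crossover subjects and 60 others contributing: the weight on d is k/(60 + k). With k = 15 this is 15/75 = 0.2, so 0.2d enters the mean. With fewer crossovers, and 60 others still contributing, it is smaller.

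These weights apply to means. Box-plot medians and quartiles also move, but not necessarily by the same amounts.

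**Step 4: share of elapsed time on placebo, if measurements fall at these weeks.**

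| Visit | Placebo weeks / total | Share | Weeks since first guselkumab |
|---|---|---|---|
| Week 20 | 16/20 | 80% | 4 |
| Week 28 | 16/28 | 57% | 12 |
| Week 40 | 16/40 | 40% | 24 |

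These are shares of time, not of bias. With a baseline at Week 16 just before the injection, the placebo share is 0 at every visit.

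**Step 5: which outputs are touched.** Only the vital-sign change statistics (7.3) and the laboratory change box plots for selected analytes (7.2), in the Placebo → Guselkumab and Combined columns. Observed values and worst NCI-CTCAE grade subtract no baseline. The eC-SSRS shift table stops at Week 16.

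**Step 6: a boundary case.** The column starts on or after the first guselkumab administration. If that is applied by date alone, a Week 16 value taken before the injection could count as post-crossover, and its change would be entirely placebo time.

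**The case against.** The best defence is that one pre-study baseline for everyone is a legitimate choice. It measures change from the state before any study injection, is the same for both arms, and agrees with the two special safety baselines. On this view Section 7 selects which measurements enter a column, Section 2.5.2 sets the reference value, and the two do not literally contradict each other. The crossover label discloses the placebo lead-in, observed values are shown beside the change, and placebo-period data are summarised separately through Week 16.

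Much of this stands as a limit on the point. It does not remove the mismatch: the columns are defined by guselkumab exposure, and the change reported in them is not. The allowance for exceptions in 2.5.2 does not help either, because no exception covers crossover.

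A reader might infer three stronger things that the SAP does not support.

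- *That a countable share of subjects would be misclassified as having shifted.* No laboratory or vital-sign shift table is planned, so one subject's weight cannot be turned into percentage points of any planned output.
- *That 80% of the Week 20 change is bias.* That figure is elapsed time. If mean drift on placebo is near zero, the column mean barely moves.
- *That a value which became abnormal on placebo is misreported throughout.* Such a value, if it persists, also appears among the observed values and, if gradable, in the worst grade. Those displays use no baseline and would be the same under either rule.

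**Conclusion.** The point holds within a narrow scope. Followed as written, the SAP puts Week 0 to Week 16 placebo change into the Placebo → Guselkumab and Combined columns of two sets of displays: vital-sign change statistics and laboratory change box plots for selected analytes. It affects at most about 15 subjects. The mean is displaced by d in the crossover column and by about 0.2d in the Combined column, with d unknown.

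This rests on three assumptions: the Section 7 column scheme, which the SAP says applies in general, is used for these displays; all 15 placebo subjects cross over and all 75 contribute at the visit (for the 0.2); and measurements are scheduled at Weeks 20, 28 and 40 (for the time shares). The measurement schedule is left to the protocol, which was not available.

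It would go too far to say that the trial's safety assessment is compromised. Adverse events, toxicity grades, eC-SSRS summaries, efficacy and the placebo-controlled comparison through Week 16 are untouched, and no hypothesis test is involved. It should be corrected because it misattributes change and is cheap to remove.

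**What to change.** Add to SAP 2.5.2, and repeat in Section 7: for crossover subjects in the Placebo → Guselkumab and Combined Guselkumab columns, baseline for laboratory and vital-sign change is the last measurement before the first guselkumab injection, and that measurement is not also counted as post-crossover. Section 7.2 needs a matching exception to its screening baseline for nonfasting glucose in those columns. Keep the current baseline for the Guselkumab column and for every summary through Week 16.

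If the sponsor prefers a single pre-study baseline, the SAP should say so and footnote both columns to state that change in crossover subjects includes 16 weeks on placebo.

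The cost is one rule, one extra derived baseline flag and a footnote, because two baseline definitions will be in use. No new data are needed if a pre-injection value exists at Week 16. Otherwise the last earlier value serves, and some placebo time remains in the change. The change is best made before the Week 20 database lock, after which the sponsor is unblinded.
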